15.19 Nursing Guidelines

- 15.191 Dosing should be based on actual weight for patients weighing ≤ 100 kg. Patients weighing greater than 100 kg, will be dosed based on 100 kg. Round doses to the nearest whole milligram.
- 15.192 DO NOT administer by IV push or bolus. Brentuximab vedotin must be given over approximately 30 minutes. Do not mix with other medications. In-line filters should not be used during infusion.
- 15.193 Cytopenias are common. Monitor CBC w/differential closely. Instruct patient to report any signs or symptoms of infection, and/or bleeding.
- 15.194 Rash is common. Rarely patients can develop Steven's Johnson Syndrome or TENS. Instruct patient to report any rash. Rash/pruritis/dermatitis is seen. Patients should report any rash to the study team. Treat per section 8.0 and monitor for effectiveness.

- 15.195 Instruct patient that sensory neuropathy is common. Assess for symptoms of neuropathy prior to each infusion and discuss with treating MD any \geq grade 2 neuropathic symptoms.
- 15.196 Fatigue is common. Discuss with patient energy conserving lifestyle and interventions.
- 15.197 GI side effects can be seen, including diarrhea, nausea, vomiting and abdominal pain. Treat symptomatically and monitor for effectiveness. Diarrhea can be common and can be very severe, leading to colonic perforation. Instruct patients to report ANY increase in the number of stools and/or change in baseline, blood in the stool, abdominal pain to the study team immediately.
- 15.198 Anaphylaxis and septic shock can be seen but are rare. Monitor for sign and symptoms of these during infusion. Administer emergency medications as ordered.
- 15.199a Monitor for respiratory symptoms (cough, URI). Treat symptomatically and monitor for effectiveness. Pneumonitis can be seen and may be mild (only seen on imaging) to severe. Patients should be instructed to report any SOB, dyspnea, cough, chest pain, etc. to the study team immediately. Patients reporting these symptoms should have a pulse ox checked and consider immediate imaging per the treating MD.
- 15.199b Assess patients medications. Patients who are taking medications that are CYP3A4 inhibitors (i.e ketoconazole) should be closely monitored for adverse reactions. Nivolumab side effects vary greatly from those of traditional chemotherapy and can vary in severity from mild to life threatening. Instruct patients to report any side effects to the study team immediately. Side effects may be immediate or delayed up to months after discontinuation of therapy. Most side effects are reversible with prompt intervention of corticosteroids. Additionally combination therapy (with ipilimumab) tends to have a higher rate of immune mediated side effects.
- 15.199c Monitor LFT's closely as elevations in these levels could indicate early onset autoimmune hepatitis. Patients should also be instructed to report any jaundice, or right upper quadrant pain to the study team immediately.
- 15.199g Endocrinopathies (including hypopituitarism, hypothyroidism, hypophysitis, new onset diabetes and adrenal insufficiency) are seen with this agent. Patients may present only with the vague sense of fatigue and "not feeling well". Additional symptoms may be that of nausea, sweating and decreased activity tolerance. Instruct patients to report these signs or symptoms immediately and obtain appropriate labs as ordered by MD.
- 15.199h Pancreatitis is possible with nivolumab. Instruct patients to report abdominal pain, nausea and vomiting to the study team.
- 15.199i Patients who are started on steroid therapy for any side effects of nivolumab toxicity should be instructed to take the steroids as ordered, and not to discontinue abruptly as symptoms may return and be severe. Patients may be on steroid therapy for weeks. Instruct patients to report

any increase or change in side effects with any dosage decrease as patients may need a slower taper.

- 15.199j Monitor renal function as patients may experience acute interstitial nephritis. Report any increase of levels to the study team.

15.2 Nivolumab (Opdivo®, BMS-936558)

- 15.21 **Background:** Nivolumab is a human immunoglobulin G4 (IgG4) monoclonal antibody that selectively inhibits programmed cell death-1 (PD-1) activity by binding to the PD-1 receptor to block the ligands PD-L1 and PD-L2 from binding. The negative PD-1 receptor signaling that regulates T-cell activation and proliferation is therefore disrupted. This releases PD-1 pathway-mediated inhibition of the immune response, including the antitumor immune response.
- 15.22 **Formulation:** Available for injection 10mg/ml (4mL, 10mL, 24mL) in a single-use vial [contains in sodium citrate, sodium chloride, mannitol, diethylenetriaminepentacetic acid (pentetic acid), polysorbate 80, and water for injection]
- 15.23 **Preparation and storage:** When the dose is based on patient weight (ie, mg/kg), nivolumab injection can be infused undiluted (10 mg/mL) or diluted with 0.9% Sodium Chloride Injection, USP or 5% Dextrose Injection, USP to concentrations as low as 0.35 mg/mL. When the dose is fixed (eg, 240 mg, 360 mg, or 480 mg flat dose), nivolumab injection can be infused undiluted or diluted so as not to exceed a total infusion volume of 160 mL. For patients weighing less than 40 kilograms (kg), the total volume of infusion must not exceed 4 mL per kg of patient weight. Mix diluted solution by gentle inversion. Do not shake. Discard partially used vials or empty vials. Store at room temperature for no more than -8 hours (includes time of administration) or under refrigeration at 2°C to 8°C (36°F-46°F) for no more than 24 hours from the time of infusion preparation. Protect from light and freezing. If stored in a glass front refrigerator, vials should be stored in the carton. Recommended safety measures for preparation and handling of nivolumab include laboratory coats and gloves. For additional details on prepared drug storage and use time of nivolumab under room temperature/light and refrigeration, please refer to the BMS-936558 (nivolumab) Investigator Brochure section for “Recommended Storage and Use Conditions”
- 15.24 **Administration:** Administer over 30 minutes through a line with a sterile, nonpyrogenic, low protein binding 0.2 to 1.2 micrometer in-line filter. It cannot be administered as an IV push or bolus injection. Do not administer other medications through the same IV line. Flush IV line at the end of the infusion.
- 15.25 **Pharmacokinetic information:**
Distribution: Vd: 8 L
Half-life elimination: ~27days
Renal Impairment: No clinically important differences in the clearance of nivolumab were found between subjects with mild or moderate renal impairment and subjects with normal renal function. Data from subjects with severe renal impairment are too limited to draw conclusions on this population.
Hepatic Impairment: No clinically important differences in the clearance of nivolumab were found between subjects with mild hepatic impairment and normal hepatic function. Nivolumab has not been studied in subjects with moderate (total bilirubin > 1.5 to 3 times ULN and any AST) or severe hepatic impairment (total bilirubin > 3 times ULN and any AST).

- 15.26 **Potential Drug Interactions:** Nivolumab is an IgG4 monoclonal antibody, which is eliminated by mechanisms similar to that of other antibodies, namely by non-specific catabolism (mainly by enzymes in the reticuloendothelial system). These enzymes are not known to be inhibited or induced by drugs, and therefore it is unlikely that other drugs will have an impact on the PK of nivolumab.
- 15.27 **Known potential toxicities:** (from package insert): Consult the package insert for the most current and complete information.

Very common known potential toxicities (>10%):

Cardiovascular: Edema ($\leq 13\%$), peripheral edema ($\leq 13\%$), hypertension (11%)

Central nervous system: Fatigue ($\leq 59\%$), malaise ($\leq 46\%$), headache (16% to 23%), dizziness ($\leq 14\%$), peripheral neuropathy ($\leq 14\%$; grade 3: $< 1\%$)

Dermatologic: Skin rash (1% to 40%; immune-mediated: 9% to 16%), pruritus (10% to 28%), vitiligo ($\leq 11\%$)

Endocrine & metabolic: Hyperglycemia (19% to 46%), hyponatremia (19% to 41%), increased serum triglycerides (32%), hyperkalemia (11% to 30%), increased thyroid stimulating hormone level ($\geq 10\%$ to 26%), hypocalcemia (10% to 26%), increased serum cholesterol (21%), hypercalcemia (2% to 19%), thyroiditis ($\leq 12\%$ to 18%; including immune-mediated events), hypomagnesemia (14% to 17%), hypokalemia (14% to 16%), thyroid dysfunction (15%), hypothyroidism ($\leq 12\%$; including immune-mediated events)

Gastrointestinal: Diarrhea (1% to 43%), nausea (20% to 34%), abdominal pain (13% to 34%), increased serum lipase (20% to 33%), decreased appetite (14% to 28%), vomiting (12% to 28%), constipation (10% to 23%), increased serum amylase (13% to 19%)

Genitourinary: Urinary tract infection (2% to 17%)

Hematologic & oncologic: Anemia (26% to 50%; grades 3/4: 3% to 8%), lymphocytopenia (27% to 42%; grades 3/4: $\leq 11\%$), leukopenia (11% to 38%; grades 3/4: $\leq 5\%$), thrombocytopenia (15% to 37%; grades 3/4: 1% to 3%), neutropenia (13% to 37%; grades 3/4: 4% to 5%)

Hepatic: Increased serum alkaline phosphatase (10% to 37%), increased serum aspartate aminotransferase (22% to 33%), increased serum alanine aminotransferase (23% to 32%), increased serum bilirubin (11% to 14%)

Immunologic: Graft versus host disease (20%; within 14 days of stem cell infusion), antibody development (11%; neutralizing: $< 1\%$)

Neuromuscular & skeletal: Asthenia ($\leq 57\%$), musculoskeletal pain (20% to 42%), back pain (21%), arthralgia (10% to 21%)

Renal: Increased serum creatinine (12% to 42%)

Respiratory: Upper respiratory tract infection (2% to 44%), cough ($\leq 36\%$), productive cough ($\leq 36\%$), dyspnea ($\leq 27\%$), dyspnea on exertion ($\leq 27\%$), bronchopneumonia ($\leq 13\%$), pneumonia ($\leq 13\%$), nasal congestion (11%)

Miscellaneous: Febrile reaction (35%; events without an infectious cause that required steroids), fever ($\leq 29\%$; may include tumor-associated fever), infusion-related reaction ($\leq 14\%$)

Cardiovascular: Pulmonary embolism (2% to 3%)

Central nervous system: Neuritis ($< 10\%$), peripheral nerve palsy (peroneal: $< 10\%$), insomnia (9%)

Dermatologic: Erythema of skin (10%), xeroderma (7%)

Endocrine & metabolic: Weight loss (7% to 8%), hyperthyroidism (3% to 6%; including immune-mediated events), adrenocortical insufficiency (1%; including immune-mediated events), increased gamma-glutamyl transferase

Gastrointestinal: Intestinal perforation ($< 10\%$), stomatitis ($< 10\%$), colitis (including immune-mediated events: $\leq 6\%$)

Hepatic: Hepatitis (immune-mediated: 2% to 3%)
 Immunologic: Sjogren's syndrome (<10%)
 Infection: Sepsis ($\geq 2\%$, systemic inflammatory response)
 Neuromuscular & skeletal: Myopathy (<10%), rheumatism (spondyloarthropathy: <10%)
 Renal: Acute renal failure ($\geq 2\%$), nephritis ($\leq 1\%$; immune-mediated), renal insufficiency ($\leq 1\%$; immune-mediated)
 Respiratory: Interstitial pulmonary disease (6%), pneumonitis ($\leq 6\%$; including immune-mediated events), pleural effusion (1% to 5%), respiratory failure ($\geq 2\%$)

Frequency not defined:

Central nervous system: Migraine

Dermatologic: Acneiform eruption, bullous dermatitis, dermatitis, erythematous rash, exfoliative dermatitis, maculopapular rash, morbilliform rash, palmar-plantar erythrodysesthesia, psoriasiform eruption, pustular rash, Stevens-Johnson syndrome, toxic epidermal necrolysis

Endocrine & metabolic: Dehydration

Gastrointestinal: Abdominal distress

Neuromuscular & skeletal: Limb pain

Rare known potential toxicities (<1%), postmarketing, and/or case reports:
 Demyelinating disease (immune-mediated), diabetic ketoacidosis, duodenitis (immune-mediated), encephalitis (limbic/lymphocytic/viral; may be immune-mediated), facial nerve paralysis (immune-mediated), gastritis (immune-mediated), Guillain-Barré syndrome, hepatic sinusoidal obstruction syndrome, hypophysitis (including immune-mediated events), immunological signs and symptoms (hemophagocytic lymphohistiocytosis) (Hantel 2018), iritis (immune-mediated), lymphadenitis (immune-mediated; histiocytic necrotizing lymphadenitis [Kikuchi lymphadenitis]), motor dysfunction (immune-mediated), myasthenia (myasthenic syndrome), myocarditis (immune-mediated), myositis (immune-mediated), neuropathy (autoimmune; immune-mediated), pancreatitis (immune-mediated), pituitary insufficiency (immune-mediated), pneumonia due to *Pneumocystis jirovecii*, polymyalgia rheumatica (immune-mediated), rhabdomyolysis (immune-mediated), sarcoidosis (immune-mediated), sixth nerve palsy (abducens nerve palsy; immune-mediated), type I diabetes mellitus (immune-mediated event), uveitis (immune-mediated), vasculitis, Vogt-Koyanagi-Harada syndrome

- 15.28 **Drug procurement:** Investigational nivolumab is provided free of charge to patients by Bristol-Myers Squibb Research and Development.

15.281 Nivolumab will be provided free of charge from Bristol-Myers Squibb for investigational use to Clinical Research Services, a division of Rx Crossroads by McKesson. Each participating ACCRU treating location will order the drug from Clinical Research Services, a division of Rx Crossroads by McKesson. Fax the Drug Order Request Form (found as a stand alone document) to:

[REDACTED]
 [REDACTED]
 [REDACTED]

Each participating ACCRU treating location will be responsible for monitoring the supply of Nivolumab and will use the appropriate Drug Order Request Form to order additional supplies as needed.

Outdated or remaining drug is to be destroyed on-site as per procedures in place at each institution.

15.29 Nursing Guidelines

- 15.291 Nivolumab side effects vary greatly from those of traditional chemotherapy and can vary in severity from mild to life threatening. Instruct patients to report any side effects to the study team immediately. Side effects may be immediate or delayed up to months after off therapy. Most side effects are reversible with prompt intervention of corticosteroids. Additionally combination therapy (with ipilimumab) tends to have a higher rate of immune mediated side effects.
- 15.292 Diarrhea can be common and can be very severe, leading to colonic perforation. Instruct patients to report ANY increase in the number of stools and/or change in baseline, blood in the stool, abdominal pain to the study team immediately.
- 15.293 Rash/pruritis/dermatitis is seen. Patients should report any rash to the study team. Treat per section 8.0 and monitor for effectiveness.
- 15.294 Monitor LFT's closely as elevations in these levels could indicate early onset autoimmune hepatitis. Patients should also be instructed to report any jaundice, or right upper quadrant pain to the study team immediately.
- 15.295 Pneumonitis can be seen and may be mild (only seen on imaging) to severe. Patients should be instructed to report any SOB, dyspnea, cough, chest pain, etc. to the study team immediately. Patients reporting these symptoms should have a pulse ox checked and consider immediate imaging per the treating MD.
- 15.296 Endocrinopathies (including hypopituitarism, hypothyroidism, hypophysitis, new onset diabetes and adrenal insufficiency) are seen with this agent. Patients may present only with the vague sense of fatigue and "not feeling well". Additional symptoms may be that of nausea, sweating and decreased activity tolerance. Instruct patients to report these signs or symptoms immediately and obtain appropriate labs as ordered by MD.
- 15.297 Pancreatitis is possible with nivolumab. Instruct patients to report abdominal pain, nausea and vomiting to the study team.
- 15.298 Patients who are started on steroid therapy for any side effects of nivolumab toxicity should be instructed to take the steroids as ordered, and not to discontinue abruptly as symptoms may return and be severe. Patients may be on steroid therapy for weeks. Instruct patients to report any increase or change in side effects with any dosage decrease as patients may need a slower taper.
- 15.199a Monitor renal function as patients may experience acute interstitial nephritis. Report any increase of levels to the study team.
- 15.199b Patients who have previously undergone a solid organ or tissue transplant and subsequently undergo therapy with nivolumab are at increased risk of organ/tissue rejection. Instruct patients that it is crucial that they stay in touch with their transplant team during treatment.
- 15.199c Patients who have undergone allogeneic BMT are at higher risk of GVHD and death when receiving nivolumab. Monitor patients closely for GVHD symptoms and instruct patients to report these symptoms to the study team immediately.

16.0 Statistical Considerations and Methodology

16.1 Overview

This is a phase II study of nivolumab and brentuximab vedotin in patients with untreated Hodgkin lymphoma ≥ 60 years old or under 60 and unable to receive standard ABVD chemotherapy. The study is designed to assess the overall metabolic response rate using a single stage phase II study design with an interim analysis. Accrual will be halted after 6 patients to assess safety (see Section 16.4). We do not plan to halt accrual during the interim analysis (see Section 16.214).

16.11 Primary Endpoint: The primary endpoint of this trial is the rate of overall metabolic response. A metabolic response is defined as a patient who has achieved an objective status of PMR or CMR at the end of cycle 8. Throughout Section 16.0, metabolic response will be considered synonymous with “success”, unless specified otherwise. All patients meeting the eligibility criteria, who have signed a consent form and have begun treatment will be evaluable for response, unless they are determined to be a major violation or are replaced in the safety analysis phase per Section 13.6. If the safety analysis determines that a reduction to the starting dose is warranted, only patients treated at the final dose level will be included when evaluating the decision rules in Sections 16.211 and 16.212. Patients treated at other dose levels will be summarized separately.

16.2 Statistical Design:

16.21 Decision Rule:

In a single-agent front-line phase II study of HL patients ≥ 60 years-old treated with brentuximab vendotin, the interim analysis of 27 patients reported rate of 93%⁶. This study will look at responses maintained until the end of cycle 8 and will utilize an updated response criteria that assesses metabolic response (Cheson 2014). Considering these factors, along with heterogeneity of disease in patients with HL and a broader eligibility criteria that includes patients < 60 years old with other co-morbidities, an overall metabolic response rate of greater than 65% for brentuximab vendotin with the addition of nivolumab would be of interest for this study.

The largest success proportion where the proposed treatment regimen would be considered ineffective in this population is 65%, and the smallest success proportion that would warrant subsequent studies with the proposed regimen in this patient population is 80%. The following one-stage design with an interim analysis is based on a two-stage Simon optimum design and requires 56 evaluable patients to test the null hypothesis that the true success proportion in this patient population is at most 65%.

16.211 Interim Analysis: Enter 25 evaluable patients into the study. If 17 or fewer successes are observed in the first 25 evaluable patients, we will consider this regimen ineffective in this patient population and terminate the study. Otherwise, if the number of successes is at least 18, we will continue accrual.

16.212 Final Decision Rule: Enter an additional 31 evaluable patients into the study. If 40 or fewer successes are observed in the first 56 evaluable patients, we will consider this regimen ineffective in this patient population and terminate this study. Otherwise, if the number of successes is at least 41, this will be considered evidence of promising activity and the treatment may be recommended for further testing in subsequent studies in this population.

16.213 Over Accrual: If more than the target number of patients are accrued, the additional patients will not be used to evaluate the stopping rule or used in any decision making process. Analyses involving over accrued patients are discussed in Section 16.313.

16.214 NOTE: We will not suspend accrual at the interim analysis to allow the first 25 patients to become evaluable, unless undue toxicity is observed. Given the limited

overall sample size and the inclusion of an adverse events stopping rule, we feel it is ethical to not halt accrual for the interim analysis. However, if accrual is extremely rapid, we may temporarily suspend accrual in order to obtain safety data on these patients before re-opening accrual to further patients.

- 16.22 **Sample Size:** The one stage study design with an interim analysis to be used is fully described above. A minimum of 25 and a maximum of 56 evaluable patients will be accrued onto this phase II study at the final dose level determined in the safety analysis phase, unless undue toxicity is encountered. An additional one or two cohorts of 6 patients will be accrued if the early safety analysis determines that a reduction to the starting dose is warranted for up to 12 additional evaluable patients. We anticipate accruing up to an additional 7 patients (2 safety analysis, 5 phase II) to account for ineligibility, cancellation, major treatment violation, or other reasons (i.e. replacement of a safety analysis patient) for a total of 75 patients overall.
- 16.23 **Accrual Rate and Study Duration:** The anticipated accrual rate is 25-30 evaluable patients per year. At this rate, it will likely take about 3 years to enroll all patients. The maximum total study duration is expected to be approximately 3.5 years, or until the last patient accrued has been observed for at least 6 months.
- 16.24 **Power and Significance Level:** Assuming that the number of successes is binomially distributed, the significance level is .10, i.e. there is a 10% chance of finding the drug to be effective when it truly is not. The probability of declaring that this regimen warrants further study (i.e. statistical power) and the probability of stopping at the interim analysis under various success proportions can be tabulated as a function of the true success proportion as shown in the following table.

If the true success proportion is...	0.65	0.70	0.75	0.80
Then the probability of declaring that the regimen warrants further study is...	0.10	0.29	0.59	0.85
And the probability of stopping at the interim analysis is...	0.69	0.49	0.27	0.11

- 16.25 **Other considerations:** Adverse events, quality/duration of response, and patterns of treatment failure observed in this study, as well as scientific discoveries or changes in standard care will be taken into account in any decision to terminate the study

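### Accrual stays open while the first 25 patients are read; closing it at the 8th confirmed failure gives the same decision and spares about 5.6 patients per futility stop at a true rate of 65%, less at higher rates

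*Combined protocol and SAP*

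**What the plan says.** Section 16.21 describes a one-stage design with an interim analysis that "is based on a two-stage Simon optimum design and requires 56 evaluable patients". The interim rule in 16.211 declares the regimen ineffective and terminates the study as follows: "If 17 or fewer successes are observed in the first 25 evaluable patients". The final rule in 16.212 asks for at least 41 successes in 56.

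The endpoint is late. Section 16.21 says: "This study will look at responses maintained until the end of cycle 8". Section 16.11 defines success as PMR or CMR at that time.

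Non-suspension is stated twice. Section 16.1 says: "We do not plan to halt accrual during the interim analysis". Section 16.214 says: "We will not suspend accrual at the interim analysis to allow the first 25 patients to become evaluable, unless undue toxicity is observed". It gives as reasons the limited sample size and the adverse event stopping rule. It also allows a temporary pause if accrual is extremely rapid, in order to obtain safety data.

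On numbers, 16.22 says: "A minimum of 25 and a maximum of 56 evaluable patients will be accrued onto this phase II study". Section 16.23 adds: "The anticipated accrual rate is 25-30 evaluable patients per year". Neither section says how many patients are expected to be enrolled when the interim result is known.

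On acting sooner, 16.25 lists "patterns of treatment failure observed in this study" among the things weighed in any decision to terminate. Section 16.51 provides reviews at least twice a year. Neither gives a number.

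**The concern.** An interim futility look is there to limit enrolment on a regimen that does not reach the target. With an endpoint read more than six months after registration and accrual left open, much of that protection is spent before the look happens.

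The plan waits for all 25 readings, yet the decision can be settled earlier. Under 13.1, patients with NMR or PMD after two cycles leave treatment, and under 13.2 later progression does the same. Some failures may therefore be known long before the end of cycle 8. From the 8th failure on, each new registration joins a study whose interim outcome is already fixed.

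**Working it through.** **Inputs.** Null and target rates 65% and 80% (16.21); interim and final rules (16.211, 16.212); accrual 25–30 per year (16.23); cycles 1–7 of 21 days and cycle 8 of 6–8 weeks (7.22); treatment start within 14 days of registration (6.36). The share of failures visible at the cycle 2 PET-CT is not in the documents and is varied as an assumption.

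**1. The plan's own table (16.24).** With X ~ Bin(25, p):
- P(stop) = P(X ≤ 17)
- P(declare) = Σ over x = 18 to 25 of P(X = x) · P(Bin(31, p) ≥ 41 − x)

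| True rate | 0.65 | 0.70 | 0.75 | 0.80 |
|---|---|---|---|---|
| Declare | 0.0973 | 0.2932 | 0.5932 | 0.8525 |
| Stop at interim | 0.6939 | 0.4882 | 0.2735 | 0.1091 |

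All eight values agree with the plan at two decimals.

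**2. Time to the primary reading.** Shortest: 7 × 21 + 42 = 189 days. Longest: 7 × 21 + 56 + 14 = 217 days.

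**3. Enrolled at the full interim read.**
- Low: 25 + 25 × 189/365.25 = 25 + 12.9 = 37.9
- High: 25 + 30 × 217/365.25 = 25 + 17.8 = 42.8

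The high end needs the fast rate, the 8-week final interval and the full start gap together. A simulation with start delay uniform on 0–14 days and the final read uniform on 189–203 days after start gives means at a futility stop of 39.0 (25 per year) and 41.8 (30 per year).

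**4. Same decision.** X ≤ 17 of 25 is the same event as 25 − X ≥ 8 failures; this holds for every X from 0 to 25. Once the 8th failure is confirmed, no later reading among the 25 can reverse it. Step 1 therefore applies unchanged.

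**5. Saving with no early failures.** Let K be the registration position of the 8th failure and q = 1 − p. Then P(K = k) = C(k−1, 7) q⁸ p^(k−8) for k = 8 to 25. If every failure is read at the same lag, the stop comes earlier by the time taken to register 25 − K patients, so the expected saving is 25 − E(K | K ≤ 25). Multiplying by P(stop) gives the average over all trials.

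| True rate | 0.65 | 0.70 | 0.75 | 0.80 |
|---|---|---|---|---|
| E(K given a stop) | 19.42 | 20.35 | 21.11 | 21.72 |
| Saved per futility stop | 5.58 | 4.65 | 3.89 | 3.28 |
| Saved, averaged over all trials | 3.88 | 2.27 | 1.06 | 0.36 |

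**6. Saving if half of the failures show at the cycle 2 PET-CT (assumption, read at six weeks).** Simulated saving per futility stop: 9.5–10.4 at 65%, 8.4–8.9 at 70%, 6.5–6.9 at 80%.

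**7. Expected size at 65%.** If accrual paused: 25 + 31 × (1 − 0.694) = 34.5. Unpaused with a full read: 44–46. With the running count: 40–42 (none early) or 37–39 (half early).

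**8. Stops below 25 enrolled, at 65%.** About 2–5% of futility stops with none early; about 14–23% with half early.

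**The case against.** The strongest reply is that nothing here is wrong. Non-suspension is stated twice with a reason, and the operating characteristics are right. That stands. A reader might infer that open accrual distorts the error rates or was left undisclosed; the documents support neither.

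A second reply is that the team can already act. Nothing in 16.211 forbids stopping once the result is certain, 16.25 and 16.51 give discretion, and 7.1 sets up a weekly investigators' call. This stands in part. The call is described under the safety analysis phase. The adverse event rule in 16.52 responds only to grade 4 or higher non-hematologic events, and the rapid-accrual pause serves safety data. None of these obliges anyone to count failures.

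A third reply concerns size. A reader might take 5.6 to 10 patients as the saving for any futility stop. It is not: both figures belong to a true rate of 65%, and the upper one also needs the assumed half share of early failures. A reader might also try to derive that share by setting the 93% response rate quoted in 16.21 against the 65% null. The documents do not support this. The 93% comes from brentuximab vedotin alone, and 16.21 itself says that this study uses a different response timing and updated criteria.

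Finally, the rule has costs. It can end enrolment below the 25 given in 16.22, and it leaves fewer patients for CMR, duration of response, PFS and the correlative work. Both points stand and should be written into the plan.

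**Conclusion.** This is a cheap, worthwhile improvement to a disclosed design choice, not an error. At the planned accrual rate, about 38–43 patients (simulated mean 39–42) will be enrolled when the first 25 are all read. A running count reaches the same decision sooner, with the false-positive rate, power and stopping probability unchanged.

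The part that needs no assumption about early failures is modest: 5.6 patients per futility stop at the null rate and about 3 to 5 at 70–80%. Over all trials that is about 3.9 patients at 65% and almost nothing at 80%, so a good regimen is hardly affected. Anything larger depends on how many failures show at cycle 2, which the documents do not say. The figures also rest on the nominal schedule, steady accrual at the planned rate, and prompt confirmation of failures.

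**What to change.** **16.211 and 16.214.** Declare futility and close accrual as soon as 8 non-successes are confirmed among the first 25 evaluable patients, in registration order, at the final dose level (16.11).
- Count a patient only after eligibility (13.7) and major-violation status (13.8) have been checked.
- Count NMR or PMD after cycle 2, later PD or PMD, and death before the end-of-cycle-8 assessment.
- Count a patient who stops early while in PMR or CMR only once end-of-cycle-8 status is known or definitively missing. This keeps the endpoint as defined.
- Collect end-of-cycle-8 status for everyone already enrolled and report all of them. The decision set is the first 25, or all enrolled if fewer.

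The change concerns accrual only. Treatment of enrolled patients stays under the existing sections.

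**16.22.** State that about 38–43 patients are expected to be enrolled at a full interim read, and that a running-count stop can end below 25.

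**16.312.** Note that the interval is approximate after such a stop.

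**Cost.** A few sentences in Section 16, a running count, and prompt eligibility and violation checks. After an early stop, the secondary and correlative estimates rest on fewer patients. No patients are added, accrual is not paused to wait for readings, and the error rates do not change.
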